### 1.2 Clinical Study Plan

Subjects of group A and C will receive MV-CHIK or control-vaccine on day 0 and 28 and placebo (saline) on day 196. Subjects of group B and D will receive placebo (saline) on day 0, MV-CHIK or control-vaccine on day 28, followed by a booster of the same vaccine on day 196. Subjects randomized to measles booster group M1 or M2 will receive the control vaccine (Priorix® MMR-Vax-Pro® or equivalent measles vaccine) as first vaccination on day -28. Group M1 will then receive two MV-CHIK high dose vaccinations on day 0 and 28, followed by two placebo injections on day 168 and 196. Group M2 will receive two placebo injections on day 0 and 28, followed by two MV-CHIK high dose vaccinations on day 168 and 196.

Figure 1 Treatment Schedule

	V s	V0	V1	V2	V3	V4	V5	V6	(V7)
	-35	-28	0	28	56	168	198	224	286
screening / enrolment	randomi- zation								
	M1 + M2 1st shot	M1 + M2 2nd shot	M1 + M2 3rd shot			M1 + M2 4th shot	M1 + M2 5th shot		
	A+B+C+D V0 + V1 together on the same day 1st shot	A+B+C+ D 2nd shot					A+B+C+ D 3rd shot		

**A + B** = low dose or Priorix 
**C + D** = high dose or Priorix 
**M1 + M2** = Priorix and high dose 
placebo 
blood collection 

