(5.1) Sites outside of Vienna: serum samples (blood 2x 8-10 mL) to be collected for additional immunogenicity analyses (cross neutralization and passive transfer)

(5.2) Vienna sites only: PBMCs will be isolated from fresh blood (blood 24-30 mL and once at V3 48-60 mL). (section 8.3.2)

(6) Hemoglobin, hematocrit, erythrocyte count, differential white blood count, platelets (EDTA blood: 3-5 mL)

(7) Prothrombin time, aPTT, fibrinogen (blood: 3-5mL)

(8) Creatinine, sodium, potassium, calcium, aspartate aminotransferase (AST), alanine aminotransferase (ALT), alkaline phosphatase, bilirubin (blood 8-10 mL),

(9) Pregnancy test will be performed for women of childbearing potential. (section 8.3.6)

(10) Glucose, protein, pH, erythrocytes, leucocytes, nitrite, ketones, urobilinogen, bilirubin and specific gravity

(11) The subjects will assess local tolerability and systemic reactions themselves over a period of 7 consecutive days after each injection. (section 11.2.5)

(12) Investigation of injection site reaction 1 hour after vaccination and additionally before each subsequent vaccination. (section 11.2.4)

(13) Shedding: only in AKH Vienna, only in a subset of group A-D, on day 0, 28, 196 and additional shedding sampling visits on day 7, 10 and 14 (±1 day each) after the first vaccination on day 0. (section 8.3.1)

(14) Only measles booster group M1 and M2

(15) women of childbearing potential will be followed up by a phone call, to ensure no pregnancy occurred 3 months after the last vaccination

\*\* Group A, B, C, and D will perform Visit 0 and Visit 1 procedures on one day, group M1 and M2 will perform V0 and V1 on two days (28 days apart)

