### 6.3 Randomization

At Visit 0, eligible subjects will be assigned to one of six treatment groups in timely order and receive a three-digit randomization number using randomization envelopes provided by data management. The site will also be provided with emergency envelopes for unblinding in case of emergency and if knowledge of the treatment assignment is mandatory for emergency treatment.

Treatment groups A, B, C and D:

All subjects will receive three i.m. injections on study day 0, 28 and 196. Subjects randomly allocated to group A or B will receive either MV-CHIK low dose or a control-vaccine (Priorix® or MMR-Vax-Pro® or equal measles vaccine). Subjects randomly allocated to group C or D will receive MV-CHIK high dose or a control-vaccine. Block randomization will be used with a randomization ratio of 1:6 (control-vaccine : MV-CHIK).

All subjects of treatment groups A, B, C and D additionally will be randomized to one of two treatment sequences. Group A + C will receive vaccinations (MV-CHIK or control vaccine) on day 0 and 28 and placebo injection on day 196 whereas groups B + D receive placebo injection on day 0 and vaccinations (MV-CHIK or control vaccine) on day 28 and 196.

Measles booster group M1 and M2:

All subjects will receive five i.m. injections and the first injection on day -28 will be the control vaccine (Priorix® or MMR-Vax-Pro® or an equal measles vaccine). Subjects will be randomly allocated to receive MV-CHIK on day 0 and on 28 (and placebo on day 168 and 196), or to receive MV-CHIK on day 168 and on 196 (and placebo on day 0 and 28). Randomization ratio between the two booster groups will be M1 : M2 = 1 : 1

Randomization of 320 subjects to one of the six treatment groups:

Group A: MV-CHIK low : control-vaccine = 60 : 10

Group B: MV-CHIK low : control-vaccine = 60 : 10

Group C: MV-CHIK high : control-vaccine = 60 : 10

Group D: MV-CHIK high : control-vaccine = 60 : 10

Group M1:M2 MV-CHIK high day 0+28 : MV-CHIK high day 168+196 = 20 : 20

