#### 8.3.2 Measles virus shedding (AKH Vienna only)

Measles virus shedding will be analyzed in a subset of subjects randomized to treatment group A, B, C or D in the study center of AKH Vienna. Subjects will be asked if they are willing to participate in the virus shedding observation, which implies three additional site visits for sample collection. The participating subjects will sign a separate informed consent that describes the additional visits and procedures of sample collection. A minimum of 30 and a maximum of 50 subjects will be included in the shedding subset.

Besides the regular visits, these subjects additionally will return to the study site on day 7 ( $\pm 1$  day), 10 ( $\pm 1$  day), and 14 ( $\pm 1$  day) after the first injection. In addition, samples of saliva, urine and whole blood (2-3 mL) will be collected at Visit 1, 2, and 5.

The samples will be analyzed by quantitative PCR (by Envigo, Huntingdon, UK) to detect measles virus RNA. Any PCR positive sample will be further tested in an in vitro infectivity assay for the presence of infectious virus.

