**Table 10 Blood sample collection:**

Test	Type of Vials	Volume	Collections
Virology (HIV, HBV, HCV) (all sites)	serum	8 – 10 mL	1x
Immunogenicity 1 and Measles Serology (all sites)	serum	2x 8 - 10 mL	5x (A-D), 7x (M1, M2)
Immunogenicity 2 (all sites except sites in Vienna)	serum	2x 8 -10 mL	5x (A-D), 7x (M1, M2)
T cell Analysis (all sites in Vienna)	(citrate tubes) PBMCs	3x 8-10 mL once 6x 8-10 mL	5x (A-D), 6x (M1, M2)
Shedding whole blood (only AKH Vienna)	EDTA	2 - 3 mL	6x (shedding analysis, A-D only)
Hematology (all sites)	EDTA	3 - 5 mL	3x
Coagulation (all sites)	citrate tubes	3 - 5 mL	3x
Clinical chemistry (all sites)	serum	8 - 10 mL	3x

The total blood volume that will be collected during the entire study:

Sites outside Vienna:	treatment group A, B, C, D: 210 – 270 mL treatment group M1 and M2: 274 – 350 mL
Site AKH in Vienna:	treatment group A, B, C, D: 286 – 368 mL treatment group M1 and M2: 330 – 420 mL
Site Tropical Medicine Vienna:	treatment group A, B, C, D: 274 – 350 mL treatment group M1 and M2: 330 – 420 mL

Laboratory values deviating from the normal ranges will be evaluated by the investigator according to the FDA Guidance for Industry. The values will be graded (mild, moderate, severe) according to the values provided. Clinically relevant deviations have to be reported as adverse events.

NCR = not clinically relevant deviation

CR = clinically relevant deviation

NA = not assessable - laboratory error.

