6.7 Measles Virus shedding

Measles virus shedding will be analyzed in a subset of subjects randomized to treatment group A, B, C or D in the study center of AKH Vienna only at Visit 1 (Day 0), Visit 2 (Day 28) and Visit (Day 196). Besides the regular visits, subjects additionally will return to the study site on Day 7, 10, and 14 after the first injection.

Following tables/listing will be provided for the Final Analysis:

- The number of subjects participating in measles virus shedding (frequency statistics). •
- The number of sample performed by visit and treatment group (frequency statistics). •
- A data listing of measles virus shedding details (incl. date of separate informed consent and samples • obtained: urine/saliva/whole blood, sample results: urine/saliva).
- The number of subjects with positive shedding results (value ≥ 20) in urine by visit and treatment group • (frequency statistics).
- The number of subjects with positive shedding results (value ≥ 20) in saliva by visit and treatment group (frequency statistics).

Page 30 of 47

PHARMACOKINETICS / PHARMACODYNAMICS ANALYSIS 7.

Not applicable for this study.

Page 31 of 47

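### Shedding samples at Days 7, 10 and 14 follow saline in groups B and D, but the SAP's MV-CHIK total counts them, and whole-blood results are left out

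*Protocol*

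**What the plan says.** **Sampling.** Protocol Table 2, note 13, sets "additional shedding sampling visits on day 7, 10 and 14 (±1 day each) after the first vaccination on day 0". Protocol Table 4 places these visits between Visit 1 (Day 0) and Visit 2 (Day 28). The Austrian schedule in SAP 1.5.3 uses the same Day 0 anchor, which matters because only AKH Vienna recruits the subset. SAP 6.7 counts from the first injection. In addition, "samples of saliva, urine and whole blood (2-3 mL) will be collected at Visit 1, 2, and 5" (Protocol 8.3.2), and Protocol Table 10 counts the blood collections as "6x (shedding analysis, A-D only".

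**Injections (Protocol 1.2).** "Subjects of group A and C will receive MV-CHIK or control-vaccine on day 0 and 28 and placebo (saline) on day 196". In contrast, "Subjects of group B and D will receive placebo (saline) on day 0, MV-CHIK or control-vaccine on day 28", with the same product again on Day 196.

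**Size and allocation.** "A minimum of 30 and a maximum of 50 subjects will be included in the shedding subset" (Protocol 8.3.2). Within groups A to D, "Block randomization will be used with a randomization ratio of 1:6 (control-vaccine : MV-CHIK" (Protocol 6.3).

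**Reporting.** SAP 2.3 shows A, B, C and D (MV-CHIK recipients) and the two control-vaccine groups CV1 and CV2 in separate columns. It adds one total for all MV-CHIK groups and one for all controls. SAP 6.7 tabulates positives in urine and in saliva by visit and treatment group, and the titles of tables 3.1.25 and 3.1.26 add an overall result. The listing in SAP 6.7 gives "sample results: urine/saliva". Listing 3.5 records whether whole blood was obtained, but gives no result.

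**The concern.** Shedding of live recombinant virus is a secondary endpoint (Protocol 4.1.2). Days 7, 10 and 14 are the only samples between an injection and the next four-week visit, so the schedule relies on them to catch early shedding. Protocol 6.2 describes the aim as shedding from immunized subjects, and Protocol 11.2 uses immunization to mean Priorix or MV-CHIK. On Days 7 to 14, B and D have had neither.

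Two things are at stake. A reader of the MV-CHIK total would see a rate that is too low over a denominator that looks too large. One of the three collected specimens would have no reported result. The protocol itself treats transmission as possible: Protocol 8.3.6 mentions potential transmission of MV-CHIK, and exclusion criterion 25 keeps out people in contact with vulnerable groups.

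**Working it through.** **1. The plan's own count.** Sampling days 0, 7, 10, 14, 28 and 196 make 6 collections, as in Table 10. At 2-3 mL each this is 6 × 2 = 12 mL to 6 × 3 = 18 mL. The stated A-D totals for AKH Vienna and the other Vienna site differ by 286 − 274 = 12 mL and 368 − 350 = 18 mL. The figures agree, so they leave no room for further blood sampling visits after Day 28 in B and D.

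**2. Time from MV-CHIK to sample (nominal days).**

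| Sample day | A, C (MV-CHIK Days 0, 28) | B, D (MV-CHIK Days 28, 196) |
|---|---|---|
| 0 | day of dose 1 | before any MV-CHIK |
| 7, 10, 14 | 7, 10, 14 after dose 1 | before any MV-CHIK; 7, 10, 14 after saline |
| 28 | 28 after dose 1; day of dose 2 | day of dose 1 |
| 196 | 196 after dose 1; 168 after dose 2 | 168 after dose 1; day of dose 2 |

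Visit windows are ±5 days at Day 28 and ±10 days at Day 196. Whether the shedding sample precedes the injection at Visits 1, 2 and 5 is not stated. No group is sampled 7 to 14 days after a second MV-CHIK dose.

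**3. Expected subset composition.** The inputs are four groups of 60 MV-CHIK + 10 control, 4 × 70 = 280. The assumption is that the subset mirrors randomization; no stratification is stated.

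| | Share | N = 30 | N = 50 |
|---|---|---|---|
| A + C on MV-CHIK | 120/280 = 43% | 12.9 | 21.4 |
| of which per dose level | 60/280 = 21% | 6.4 | 10.7 |
| B + D on MV-CHIK | 120/280 = 43% | 12.9 | 21.4 |
| Control vaccine | 40/280 = 14% | 4.3 | 7.1 |

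The 95% hypergeometric range for A + C on MV-CHIK is 8 to 18 of 30, or 15 to 28 of 50. B + D including controls are expected to be 140/280 = 50% (range 10 to 20 of 30, or 19 to 31 of 50).

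**4. Precision with no positives.** The one-sided 95% upper limit is 1 − 0.05^(1/n):
- both dose levels together: n = 13 gives 20.6%, n = 21 gives 13.3%;
- one dose level: n = 6 gives 39.3%, n = 11 gives 23.8%.

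**5. Dilution of the MV-CHIK total at Days 7, 10 and 14.** SAP 2.6 takes percentages over non-missing observations, so post-saline samples stay in the denominator. M1 and M2 are not in the subset and add nothing. With a true post-dose rate p and no positives after saline, the expected total is p × 12.9/(12.9 + 12.9) = p/2. As an illustration, a true 10% would read as 5%. The control total has the same feature, because CV2 also receives saline on Day 0.

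**6. Specimens.** Protocol 8.3.2 and Table 4 collect urine, saliva and whole blood at all six time points, and 8.3.2 sends the samples to PCR for measles virus RNA. SAP 6.7 and listing 3.5 give results for two of the three.

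**The case against.** The schedule has a fair defence. Common sampling days protect the blinding of the sequence, and Protocol 6.2 gives saline a role both in blinding and in measuring absolute differences. The B and D samples at Days 7 to 14 are useful concurrent saline controls. The by-group columns show the A and C rates undiluted and already split out the control-vaccine recipients. The endpoint runs only to Day 196, and it is descriptive, in a one-site subset of a trial without a formal sample size calculation.

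All of that stands, and it supports leaving the visits where they are. It does not rescue the MV-CHIK total, because neither document labels the B and D samples as controls and SAP 2.3 pools them as vaccinated. It also does not explain the missing whole-blood results.

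Two stronger inferences are tempting:

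- A reader might conclude that half the subset yields no shedding data after MV-CHIK. The documents do not support this. B and D are sampled on Day 196, about 168 days after dose 1, and the order of sampling and injection on Day 28 is open. Also, half is an expectation, not a designed share.
- A reader might think that moving the extra visits to follow Day 28 would double the information. First-dose data would then come only from B and D on MV-CHIK, again about 13 to 21 subjects. A count of 26 to 43 arises only by pooling first and second doses, for which a common shedding rate is not established. The move would also give up first-dose samples in A and C and every Day 7-14 sample after saline.

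**Conclusion.** The point holds as a reporting defect with a limit on information. B and D have no sample in the 1 to 28 days after an MV-CHIK dose. About 13 to 21 MV-CHIK recipients, or 6 to 11 per dose level, are expected to have 7-14 day data, so even a clean result would leave shedding rates up to about 21% to 13% unexcluded. The MV-CHIK total at those visits is expected to show about half the true post-dose rate.

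These sizes assume a subset that mirrors the 60:10 allocation across four equal groups. The halving also assumes no positives after saline. The separate A and C columns are sound, so the shedding analysis as a whole is not invalid. The omission of whole-blood results needs no assumption; it follows from setting Protocol 8.3.2 beside SAP 6.7.

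**What to change.** Change SAP 6.7, tables 3.1.25 and 3.1.26, and listing 3.5:

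- In the MV-CHIK total, count only samples taken after an MV-CHIK injection. State how samples on a dosing day (Visits 1, 2 and 5) are classified.
- Label the B and D samples at Days 7, 10 and 14 as post-placebo and show them separately as saline controls.
- Keep control-vaccine recipients separate as active comparators. The control vaccine also contains live measles virus (Protocol 5.1.2), and the PCR detects measles RNA, so they are not negative controls. Within them, mark CV2 at Days 7 to 14 as post-placebo too.
- State the informative number at each visit, expected to be about 13 to 21 at Days 7 to 14, with its upper confidence limit.
- Add a whole-blood results table and listing column, or state why there are none.

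The cost is SAP wording and some table programming. No visit, sample or protocol amendment is needed, and the blind is unaffected. The small number of early post-dose samples cannot be cured this way; it can only be reported plainly.

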## 2 INTRODUCTION

### 2.1 Disease Background

Chikungunya virus (CHIKV), a mosquito-borne pathogen that causes Chikungunya fever (CHIKF), has been spreading throughout Asia, Africa, and parts of Europe in recent times. (Enserik 2008; Rezza 2007; Wang 2008) Formerly indigenous to tropical Africa, recent large outbreaks have been reported in parts of South East Asia and due to global travel, the risk of spreading CHIKV in non-endemic regions, such as Europe and the United States, has increased. (Jain 2008)

CHIKV transmits to humans primarily by *Aedes aegypti* (Tsetsarkin 2007) and *Ae.albopictus*, which are common in many non-tropic urban areas. (Vazeille 2007). Transmission of the virus can occur in an urban cycle whereby the mosquito spreads the disease from an infected human to an uninfected human, following an epidemiological pattern similar to dengue fever (Jain 2008). Even vertical transmission of CHIKV from mother to fetus, causing congenital illness and fetal death, seems possible. (Ramful 2007; Gerardin 2008).

Most individuals will present with symptomatic disease after an incubation period of three to seven days (range, 2-12 days). Not all individuals infected with the virus will develop symptoms, approximately 3%-25% of persons with antibodies to Chikungunya virus have asymptomatic infections. However, individuals acutely infected with Chikungunya virus, whether clinically apparent or asymptomatic, can contribute to the transmission of the disease if active vectors are present.

Acute disease is mostly characterized by the acute onset of high fever (>102°F/ 39°C). The fevers typically last from several days up to two weeks. Other signs and symptoms may include headache, diffuse back pain, myalgias, nausea, vomiting, polyarthritits, rash, and conjunctivitis. After the onset of fever, the majority of infected persons develop severe, often debilitating polyarthralgias. Joint symptoms are usually symmetric and occur most commonly in wrists, elbows, fingers, knees, and ankles but also more proximal joints. The lower extremity arthralgias can be severely disabling resulting in slow, broad based, halting gait, which can persist for months. The patients suffer from severe pain, tenderness, swelling and stiffness and they cannot perform normal tasks or go to work.

During the La Reunion Epidemic a number of unusual clinical presentations were observed, including hepatitis, autoimmune neurologic pathologies (Guillain-Barré), cardiologic manifestations and death. The case fatality ratio (CFR) during the 2006 La Reunion epidemic has been estimated to be 1:1000 (0,1%), with most deaths occurring in neonates, adults with underlying medical conditions and older people (>65 years) (Staples JE, 2009). During an

epidemic in Mauritius (2005-2006) and India (2006) a CFR of 4.5% and 4.9% was reported. The difference in fatality rates can be explained by difference in pathogenicity of the viral strains causing the epidemic, but also by the difference in medical care of infected patients (Renault P, 2008). Calculated estimates from annualized averages over combined epidemic and interepidemic periods suggest 33 to 26K deaths annually attributed to Chikungunya fever. Up to 46K patients per year can develop a chronic infection (LaBeaud AD, 2011).

Acute symptoms of Chikungunya fever typically resolve within 7 to 10 days. Following the acute phase, a number of patients develop prolonged symptoms lasting several weeks to months including fatigue, incapacitating joint pain, and tenosynovitis or edemous polyarthritits of their digits. Chronic disease is defined by symptoms that persist for more than three months (CDC/PAHO Chikungunya virus, 2011).

The frequency of persons reporting persistent symptoms varies substantially by study and the time that had elapsed between symptom onset and follow-up. Studies from South Africa note that 12%–18% of patients will have persistent symptoms at 18 months and up to 2 to 3 years later. More recent studies in India revealed that the proportion of patients with persistent symptoms at 9-12 months was 22% and additional 22% reported symptoms for more than 1 year (Paul BJ, 2011). Data from La Réunion have found that as many as 60% of patients complained of persistent symptoms 36 months after disease onset. In almost one half of these patients the joint pain had negative impact on their everyday life and on their ability to work (Schilte C, 2013).

During 2005-2006 several European countries reported imported cases from travelers returning from the Indian Ocean region including France (808 imported cases). A detailed follow up of 47 patients that returned to Marseilles. 38 patients remained symptomatic after the tenth day with severe joint pain and tenosynovitis with a dramatically limited ability to ambulate and carry out activities in daily life (Simon F, 2007).

## **2.2 Investigational Drug**

The vaccine includes a backbone of measles virus (Schwarz Vaccine strain), which has been developed at the Institute Pasteur (Combredet C. 2003). Chikungunya Virus structural proteins have been inserted into the MV genome (MV-CHIK) and are expressed as the vaccine antigens. The backbone has already been tested in previous trials of MV-HIV construct (Lorin C. 2004; Stebbings R. 2012; ClinicalTrials.gov Identifier: NCT01320176). A detailed description of the vaccine construct and mechanism of action can be found in the investigators' brochure.

## 2.3 Preclinical Studies

Immunogenicity of MV-CHIK and protective effects against infection have previously been demonstrated in a series of preclinical studies in mice and cynomolgous monkeys. These experiments are described in more detail in the investigators' brochure.

## 2.4 Phase 1 Study

A Phase 1 study has been conducted in Austria at the Medical University, Vienna, Department of Clinical Pharmacology (EudraCT: 2013-001084-23):

*Observer blinded, block-randomized, active and placebo-controlled, dose escalation trial to evaluate the optimal dose of MV-CHIK, a new vaccine against Chikungunya virus, in regard to immunogenicity, safety and tolerability in healthy volunteers.*

The purpose of this first-in-man study was to evaluate the optimal dose considering immunogenicity, safety and tolerability of the MV-CHIK vaccine. We further analyzed the immunogenicity, safety and tolerability of MV-CHIK during the vaccination period up to 28 days after the last vaccination.

Each subject received an i.m. injection of one of the doses of MV-CHIK on Day 0 and either an i.m. injection with MV-CHIK on Day 28 and an i.m. injection with placebo control on Day 90 or the other way round (placebo control on Day 28 and MV-CHIK on Day 90).

Doses (volumes administered):

Cohort #1: 0.05 mL;  $1,5 \times 10^4$  ( $\pm 0,5 \times 10^4$ ) TCID50

Cohort #2: 0.25 mL;  $7,5 \times 10^4$  ( $\pm 2,7 \times 10^4$ ) TCID50

Cohort #3: 1 mL;  $3,0 \times 10^5$  ( $\pm 1,1 \times 10^5$ ) TCID50

A control group received Priorix®, an approved Measles, Mumps, Rubella vaccine that contains the parental measles vaccine Schwarz strain. Sterile saline has been injected as placebo treatment. The Phase 1 clinical batch was present at a ready to use liquid formulation at a single concentration. In contrast, the proposed Phase 2 clinical trial IMP will be presented as lyophilized product.

Out of 44 healthy male or female volunteers screened 42 subjects (98% (41/42) Caucasians, 55% (23/42) female, mean age  $30.5 \pm 7.3$  years) have been enrolled into the study from November 2013 to June 2014.

